### **C13. Data Analysis Plan: C13a. Quantitative Data Analysis Plan**

**Data screening.** Via frequency distributions and scatterplots, variables will be examined for unusual distributions, out-of-range, and extreme values. We will confirm randomization using chi-square tests, t-tests, and the Kruskal-Wallis nonparametric test. We will test assumptions and underlying statistical models during model fitting. For generalized linear models and multilevel models, we will examine the homogeneity of error, normality of residuals, linearity of relationships between independent and dependent variables, and outliers. For multilevel models, we will assess multivariate normality of random effects.

**Missing data.** All analyses will adhere to the intention-to-treat approach, which includes all participants assigned to their condition regardless of study completion (Wells, 1999). Multiple imputation (MI), an optimal technique for missing data (Graham, 2009), will include all participants and available data. For all MI analyses, 20 data sets containing plausible values for missing data will be constructed using the Amelia II package for R, which incorporates both cross-sectional and longitudinal information in data imputation (Honaker, King, Blackwell, 2012). Each data set will be analyzed separately and model parameters combined for inferential tests (Rubin, 1987). The missing at random assumption will be assessed using a sensitivity analysis in which a series of pattern-mixture models that adjust parameter estimates for missing data patterns (Hedeker & Gibbons, 1997), will be compared with basic models to identify any potentially non-ignorable missing data patterns.

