**Aim 1: Hypotheses:** Tailored implementation will outperform standardized in terms of (H1a) fidelity. MBC clinician fidelity was evaluated with two variables: (1) whether the PHQ-9 was recorded in the EHR, and (2) among encounters for which the PHQ-9 was recorded, whether it was discussed. Both outcomes were modeled using generalized linear mixed models with a logit link function for a binary distribution using the lme4 package. All models included random intercepts for clinicians and patients. Models for both outcomes were constructed in an identical sequence. Models comparisons in the model-building sequence described below were evaluated using the Bayesian Information Criterion (BIC); the model with the better BIC was selected for presentation. Several unconditional growth models (i.e., models with only parameters for time) were fit (i.e., linear, quadratic, log-transformed number of months). After establishing the unconditional growth model, additional fixed effects were added in the following sequence: (1) group main effect and (2) group x time interaction. Finally, new versus existing patient status was investigated as a main effect using a dummy variable for new patient status and as a patient status x group interaction.

**Aim 2: Hypotheses:** Contextual mediators will be leveraged in the tailored condition, but serve as barriers in the standardized condition. Mediation models were fit to evaluate which contextual factors (based on clinician-completed surveys, Table 5; and, clinician selection of drop-down menu reasons for MBC deviations captured in the electronic health record) mediate the impact of the implementation condition on both clinician- and client-level outcomes. The two critical effects underlying mediation were evaluated in separate models: treatment condition predicts the mediator (path *a*) and the mediator predicts the outcome (path *b*). Specifically, mediators were assessed at the conclusion of the implementation window and the mediators were used to predict PHQ9 completion in the sustainment window. The *a* path was assessed using linear mixed models with Satterthwaite degrees of freedom

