implemented using the R lmerTest package with a random intercept for clinic. The b path was assessed using generalized linear mixed models with a logit link function for a binary distribution using the lme4 package. **Aim 3 Hypotheses:** Adapted MBC protocols (i.e., tailored condition) will outperform routine weekly administration of PHQ-9s (i.e., standardized condition) with respect to clinically significant change in depression severity from intake to week 12. Depression severity was analyzed using linear mixed models with Satterthwaite degrees of freedom implemented using the R lmerTest package. Multiple imputation was used to estimate missing values across 20 datasets in which 22.8% of patients did not complete the 12-week interview. We first assessed whether there was a change in PHQ-9 between intake and week 12 in a mixed model containing patient status as a covariate and random intercepts for patient and clinic. Next, implementation group was added to the model. In addition, number of sessions, number of sessions that the PHQ-9 was recorded, and number of sessions that the PHQ-9 was discussed were added to the model. We also examined the interactions between new patient status and the focal variables. **Power calculations.** A power analysis for the multilevel models for Aim 1 was assessed with Monte Carlo studies in which power is the proportion of significant effects (2-tailed  $\alpha$ ,  $p < .05$ ) for parameters of interest observed over repeated analyses of simulated data (Muthén & Muthén, 2002; Thoemmes, Reiser, & MacKinnon, 2010) using MPlus (version 7). For each model, 10,000 data sets were simulated and analyzed. Data in the Monte Carlo studies were simulated with the goal of identifying the smallest detectable effect size with power  $> 80$ . Dropout was simulated to reflect an increase of 5% missing data per wave. Repeated measurements were nested within participants (ICC = .50) and participants were nested in sites (ICC = .05). Average effect sizes for Aim 1 analyses were computed using an approximation of Cohen's  $d$  for growth models (Feingold, 2009). Using this metric, we are sufficiently powered to detect effect sizes as small as  $d = .46$  for the clinician models ( $N = 150$ ) and effect sizes as small as  $d = .30$  for the client models ( $N = 500$ ). For Aim 2, we conducted power analyses for the hypothesized mediation effects with the same assumptions described above but with the use of effective samples size estimates (an ICC corrected sample size) based on a design effect adjustment (Bickel, 2007) in order to use standard effect size metrics. The  $\kappa^2$  effect size for mediation (.01, .09, and .25 represent small, medium, and large  $\kappa^2$  respectively) was computed (Preacher & Kelly, 2011). We are sufficiently powered to detect effect sizes as small as  $\kappa^2 = .16$  for the clinician models and effect sizes as small as  $\kappa^2 = .10$  for the client models. For Aim 3 analyses, we are sufficiently powered to detect effect sizes as small as  $r = .27$  for clinicians and as small as  $r = .21$  for clients. The planned sample sizes are consistently sufficient for detecting medium effect sizes for clinician outcomes and small effect sizes for client outcomes, with the power to treat site as a random effect based 6 sites per condition (Atkins & Baldwin, 2013).

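### The Aim 3 depression model adds implementation group with no group x time term and no intake adjustment, so as written it does not test differential change from intake to week 12.

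*Combined protocol and SAP*

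**What the plan says.** In A. Specific Aims and again in C13a, H3 predicts that the tailored condition will do better on clinically significant change in depression between intake and week 12. The Aim 3 analysis proceeds in steps:

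- "We first assessed whether there was a change in PHQ-9 between intake and week 12", using a "mixed model containing patient status as a covariate and random intercepts for patient and clinic".
- "Next, implementation group was added to the model".
- Counts of sessions, and of sessions with the PHQ-9 recorded or discussed, are then added.
- "We also examined the interactions between new patient status and the focal variables".

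The interactions with patient status are the only ones named. For fidelity, under Aim 1 of the same section, "additional fixed effects were added in the following sequence: (1) group main effect and (2) group x time interaction". The Aim 3 text is in the past tense and reports that "22.8% of patients did not complete the 12-week interview".

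A. Specific Aims makes Aim 1 co-primary (H1a fidelity, H1b client depression) and calls Aims 2 and 3 secondary and exploratory. The Aim 1 analysis text covers H1a only, so H1b has no labelled model.

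**The concern.** A patient random intercept needs more than one row per patient, so intake and week-12 PHQ-9 are both responses. In such a model a group main effect is a difference in level averaged over the two occasions. It is not a difference in change.

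Two errors could follow. A null result could arise because the effect was halved. C14 says that an unsupported hypothesis would show that customization harms outcomes, so such a null could be read as evidence against tailoring. In the other direction, an intake difference that persists would be counted as benefit or harm.

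This is also the only direct comparison of depression by condition in the analysis plan. If it is meant to serve H1b, the co-primary client question has no stated test of depression reduction. That link is an inference, because the plan labels the model Aim 3.

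**Working it through.** **The plan's own figure.** The power paragraph of C13a gives r = .21 as detectable for Aim 3 clients. With 625 clients, 12 sites and ICC .05, the design effect is 1 + (625/12 − 1) × .05 = 3.554 and the effective n is 175.8. Fisher's z at 80% power then gives r = .210, so the figure reproduces. It concerns a correlation and does not bear on the form of the model.

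**What the coefficient estimates.** Let D0 and D1 be the arm differences at intake and week 12. With time and group but no interaction, the group coefficient is (D0 + D1)/2 = D0 + (D1 − D0)/2. H3 concerns D1 − D0. In 40 simulated trials (12 sites × 42 clients; patient and clinic intercepts) the fitted coefficient equalled this average to within 2e-15. With unequal sites and a patient-status covariate, a true −0.30 still gave about −0.16 for group and −0.28 for group x time.

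**Inputs.** From the plan: 500 clients, 6 sites per condition, within-person ICC .50, site ICC .05, two-sided .05. Assumed: total SD 1, the .50 read as site plus patient variance, and no attrition effect beyond imputation. The effect d = .30 is the plan's detectable client effect for Aim 1.

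**As written.** Var = 2 × [s/6 + ((.50 − s) + .25)/250], where s is the site variance; the coefficient is .30/2 = .15.

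| Case | SE | Power z / t (10 df) |
|---|---|---|
| s = .05 | .149 | .17 / .15 |
| s = .02 | .112 | .27 / .23 |
| s = 0 | .077 | .49 / .42 |
| s = .05, intake SD .8 of week-12 SD | .134 | .20 / .17 |
| s = .05, intake SD .6 of week-12 SD | .120 | .24 / .21 |

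The last two rows allow for the narrower intake range implied by the PHQ-9 entry threshold: Var = 2 × [.05(1 + k)²/24 + (.95k² + .95 + .9k)/1000], where k is the SD ratio. With 625 × .772 = 483 clients and s = .05, power is again .17/.15.

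**Tests that target H3, at d = .30.** Let c be the site variance of change, which the documents do not give.

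- Change contrast: Var = 2 × (c/6 + 1/250).
- Week 12 adjusted for intake: slope .45/.95 = .474, residual variance .95 − .45²/.95 = .737, site residual .05 × (1 − .474)² + c.

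| c | Change: SE, power z / t | Intake-adjusted: SE, power z / t |
|---|---|---|
| 0 | .089, .92 / .86 | .103, .83 / .75 |
| .01 | .107, .80 / .72 | .118, .72 / .63 |
| .025 | .128, .65 / .56 | .137, .59 / .51 |
| .05 | .157, .48 / .41 | .165, .44 / .38 |

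Simulation of 8,000 trials per cell agreed: as-written power was .149, and at c = 0 the two alternatives had .860 and .746.

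**Persistent intake shift, no true effect.** Simulated rejection rates at a nominal 5%; the shift sizes are assumed.

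| Shift (SD) | As written | Intake-adjusted |
|---|---|---|
| .05 | .059 | .053 |
| .10 | .092 | .075 |
| .15 | .149 | .106 |
| .20 | .238 | .154 |
| .30 | .443 | .289 |

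The change contrast stayed at .050 to .053. If a shift faded towards the mean, the change contrast would pick up the fading.

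Effects can also cancel. With an intake difference of +.15 and a true difference in change of −.30, the as-written coefficient averaged 0.00 and rejected in about 5% of trials.

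**The case against.** The strongest reply is that the text is shorthand. It never lists the fixed effects, and even time is only implied. Group and the session counts are added to a model framed as a test of change, and the counts make most sense as predictors of change. The power paragraph also points to a change contrast: "Average effect sizes for Aim 1 analyses were computed using an approximation" for growth models. All this makes it possible that group x time was fitted and not written down. It does not make the stated sequence a test of H3, and the same section does spell the term out for fidelity. The baseline checks ("We will confirm randomization using chi-square tests, t-tests") add no term to the model.

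Other points stand in part:

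- **Status.** Aim 3 is exploratory by its own label, and the growth-model power text suggests that a separate Aim 1 client model was once intended. That model is not in the analysis text.
- **Effect size.** d = .30 belongs to Aim 1. If Aim 3's r = .21 is read as a two-group effect, d = 2 × .21/√(1 − .21²) = .43. As-written power is then .30/.26 at site ICC .05, .48/.41 at .02 and .79/.71 at 0. The loss is smaller in places, but the coefficient is still halved.
- **Intake shifts.** The documents give no size for one, and the evidence is mixed. Sites are matched and randomized, Section XII describes daily record queries with a phone screen before the first session, and the model adjusts for patient status. Against that, C12b has intake clinicians identifying clients, Section V places client recruitment after site randomization, and C12b requires new clients while Section V does not. Chance site imbalance is already covered by the clinic intercept.

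**Conclusion.** The concern holds, and the analysis text is wrong as written: the stated group coefficient does not estimate H3's differential change, and no other stated analysis does. The halving under balanced intake is algebra and does not depend on the variance assumptions when both occasions are complete. The power loss does depend on them: under the plan's ICCs and d = .30, power is about .15 to .17, rising to at most .49 if sites do not differ at all. The false-positive rates are conditional on assumed shifts and show what could happen, not what did. Confidence is medium, because the term may have been fitted and left unreported, and because the bearing on H1b is inferred.

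**What to change.** State the H3 test, and name it as the H1b test if that is intended, as one of:

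- **(a)** Week-12 PHQ-9 on intake PHQ-9, group and patient status, with a clinic random intercept and Satterthwaite degrees of freedom.
- **(b)** Group x time in the two-occasion model, with site variation in change allowed for or checked. The check could be a clinic-level time slope or, if that is poorly estimated with 12 sites, a comparison of the 12 site-mean changes on 10 df. With a clinic intercept alone, simulated type I error was .051, .100, .166 and .259 at assumed site variances of change of 0, .01, .025 and .05.

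Option (a) removes only part of a persistent intake shift, so intake means by arm should be reported either way. Inference should rest on the group model before the session and PHQ-9 counts are added. Those counts arise after randomization, so models that include them should be labelled exploratory. If group x time was in fact fitted, the text should say so. These options cover mean change; if H3 means the five-point criterion in C4, that outcome needs its own statement.

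The cost is a short edit to C13a and a re-run on existing data. Because week-12 missingness is already reported, the change must be disclosed as a correction made after data were seen. Power for the correct test may fall below 80% if sites differ in change.

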## **Phase 2 (Months 8-38)**

*Client's Treatment (weeks 0-11).* Clients in the standardized condition will be asked to complete the hard copy PHQ-9 forms in the waiting room prior to every session with their enrolled study clinician, while clients in the tailored condition will complete the PHQ-9 according to the measurement-based care guidelines defined by the implementation team at each site. In all cases, clients will fill out the hard copy PHQ-9 prior to a session located in waiting room kiosks and completing the survey should only take about five to ten minutes. The client will then hand the completed PHQ-9 to his or her clinicians who will then enter it into the electronic health record so that the clinicians can review the PHQ-9 scores with the clients during the session. The CRI RA will pull the PHQ-9 data for all enrolled clients across the course of their treatment and provide it to the research team using the 9-digit anonymous identification number. In addition to the PHQ-9, clients will be asked to respond to a telephone or text message-based survey after each psychotherapy session to inquire as to whether their clinician discussed PHQ-9 scores in the session immediately preceding (Yes/No/NA) (Appendix C.4). Client can earn \$2 for every survey they complete for up to \$20. So clients may be able to earn an additional \$20 for completing these surveys after each session and the amount attained will be mailed with the \$10 incentive for completing the week 12 PHQ-9 (described below).

*Client's Treatment (week 12).* Clients will be reassessed for depression symptom severity via a phone interview (like the initial screen) at week 12 of their treatment, regardless of number of treatment sessions attended (Appendix C.2). A postcard reminder may be sent to clients before the phone interview as a reminder. The project coordinator and CRI RAs will track client time since entering treatment, beginning with the intake assessment. Clients will be mailed \$20 as an incentive for completing the week 12 assessment.

*Client's Treatment (week 13 and beyond).* Upon completion of the telephone assessment at week 12, PHQ-9 data collection for all enrolled clients will continue to occur according to the site guidelines for the duration of the study funding-period.

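### The Aim 3 depression model adds post-randomisation session and PHQ-9 counts to the model holding implementation group, and the plan does not say which step gives the arm effect

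*Combined protocol and SAP*

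**What the plan says.** The Aim 3 text in C13a builds one linear mixed model for depression severity in three steps.

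- Step 1: "We first assessed whether there was a change in PHQ-9 between intake and week 12 in a mixed model containing patient status as a covariate", with random intercepts for patient and clinic.
- Step 2: "Next, implementation group was added to the model".
- Step 3: "In addition, number of sessions, number of sessions that the PHQ-9 was recorded, and number of sessions that the PHQ-9 was discussed were added".

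No step is named as the test of the arm hypothesis. Aim 1 has a selection rule (BIC); Aim 3 has none. The counts have no stated start or end.

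Four other places bear on this.

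- Section VII (Clients, Phase 2) shows that the arms set different PHQ-9 frequencies: "Clients in the standardized condition will be asked to complete the hard copy PHQ-9 forms in the waiting room prior to every session", "while clients in the tailored condition will complete the PHQ-9 according to the measurement-based care guidelines defined by the implementation team at each site". C10 gives monthly and every other session as examples of a site guideline.
- The same section obtains the outcome "at week 12 of their treatment, regardless of number of treatment sessions attended". After that, "PHQ-9 data collection for all enrolled clients will continue to occur according to the site guidelines for the duration of the study funding-period".
- C13a (Missing data) commits all analyses to intention to treat, which "includes all participants assigned to their condition regardless of study completion".
- Section A makes client depression severity (H1b) part of the co-primary aim. It describes Aim 3 as a secondary, exploratory look at fidelity and client outcome, yet words H3 as a comparison of arms. The Aim 1 text in C13a specifies models for fidelity (H1a) only, so the Aim 3 model is the only depression analysis specified.

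**The concern.** A randomised comparison keeps its meaning only if the model does not condition on what the arms go on to change. Here the arms differ by design in how often the PHQ-9 is due, and the third step holds constant how often it was recorded. C8 says the trial will test whether adapting MBC to the site weakens its effect. If a lower PHQ-9 frequency is how that would happen, adjusting for frequency removes the effect under study.

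A second route needs no true effect of frequency. If something about the client raises PHQ-9 completion and also predicts recovery, then clients with the same recorded count in arms with different guidelines are not alike. The group coefficient picks up that difference. The same can happen through number of sessions if the arms differ in sessions attended.

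At stake is whether the tailored-versus-standardized statement on a co-primary client outcome rests on the randomised contrast or on a conditional one. The two can differ in size and sign.

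**Working it through.** No figure in the plan is in dispute, so there is none to reproduce. The check has two parts.

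**1. Status of each term**

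| Term | When fixed | Set by the arm? | Role elsewhere |
|---|---|---|---|
| Implementation group | Site randomisation | It is the arm | Exposure in H1a, H1b, H3 |
| Number of sessions | During treatment | Possibly | None stated |
| Sessions with PHQ-9 recorded | During treatment | Yes, through the guideline | Aim 1 outcome |
| Sessions with PHQ-9 discussed | During treatment | Yes, through recording and consultation | Aim 1 outcome |

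The step 2 coefficient compares clients as randomised. The step 3 coefficient compares them at equal values of three variables that follow randomisation, two of which are outcomes of the arm.

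**2. What the adjustment can do (illustrations; all inputs assumed)**

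*An effect carried by recording.* If each recorded PHQ-9 changes the outcome by b, and the arm acts in no other way:

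total arm effect = b × (mean recorded, tailored − mean recorded, standardized).

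With counts in the model, the group coefficient should be 0. Take mean 7 sessions and 60% completion when due, with negative values meaning improvement in SD units.

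- Tailored monthly (one session in four): 7 × 0.6 × 0.25 = 1.05 against 7 × 0.6 = 4.2, difference -3.15. With b = -0.06 the total is +0.19. Simulated with 500 clients in 12 sites: 0.18 without counts, -0.01 with.
- Tailored every other session: 2.1 against 4.2, difference -2.1, total +0.13. Simulated: 0.12 and 0.00.
- Tailored records more (60% against 30%, b = -0.10): difference +2.1, total -0.21. Simulated: -0.21 and 0.00.

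In PHQ-9 points, with mean 6 sessions and 70% recorded in standardized against 35% in tailored, the difference is 6 × (0.35 − 0.70) = -2.1 records. At b = -0.3 to -0.5 the total is 0.63 to 1.05 points against tailored. Simulation gave 0.60 to 0.98 without counts and about 0 with them.

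*No arm effect, but completion shares a prognostic factor with outcome.* Here engagement raises completion and is worth 1 to 2 points per SD, the residual SD is 5.5 points and there is no site effect. The coefficient without counts is about 0. With counts, in points (negative favours tailored):

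| Recorded, standardized v tailored | Group coefficient with counts |
|---|---|
| 70% v 35% | about -0.7 to -1.4 (rejection about 21% to 65%, nominal 5%) |
| 50% v 40% | about -0.2 to -0.4 (rejection 6% to 11%) |
| Equal | 0 |
| 40% v 50% | up to about +0.4 |

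These point-scale figures treat the outcome as a change score. The Aim 3 text mentions no group-by-time term. If the coefficient is instead a shift in the average of intake and week 12, the 70% v 35% bias falls to about -0.4 to -0.7 points (rejection 10% to 21%).

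*No arm effect, but the arm shifts number of sessions.* A shift of about 0.5 to 1.4 sessions, where sessions share a prognostic factor with outcome, gave a spurious 0.05 to 0.15 SD with counts and about 0 without.

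*A harmless case.* Tailored is monthly, recording has no effect and is unrelated to prognosis given sessions, and sessions do not differ by arm. The coefficient was -0.30 without counts and -0.29 with. The cost is precision: the variance inflation of the group term was 2.5, a standard error factor of √2.5 ≈ 1.6 before any change in residual variance.

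**The case against.** The strongest reply is that the right contrast is already in the sequence. Group enters before the counts, so an arm estimate free of them exists at step 2 and no model needs reordering. Entering fidelity counts also does what Aim 3 says it will do, in an aim already labelled exploratory. Separate Aim 1 power for client growth models (d = .30) suggests that a client-level arm analysis was envisaged apart from Aim 3. All of this stands. It limits the point to the last step and to the missing statement of which step answers H1b/H3. It does not remove the point, because H3 is itself an arm comparison and no other depression model is specified.

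A reader might infer more than the documents support.

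- That the reported arm effect is the adjusted one. The plan does not say so; it leaves the choice open.
- That the plan breaks its own intention-to-treat rule. That rule concerns who is included, and adding covariates excludes nobody. The issue is what the coefficient means.
- That number of sessions measures treatment stopping, or that clients who remain depressed stay longer. The plan gives the count neither meaning; visit frequency and missed visits also affect it.
- That sessions after week 12 were used. The text on later capture describes data collection. The plan is only silent on the window.
- That the adjustment favours tailored. The sign follows the recording contrast, and H1a expects better fidelity in tailored. The tailored guidelines are not known in advance, and the only local use rates given are the pilot's 13.4% and 38.6% (C9), before tablets.

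**Conclusion.** The point holds for the last step of the Aim 3 model. Its group coefficient is not the total effect of tailored versus standardized implementation, and the plan does not prevent it from being read as the test of H1b or H3. That conclusion follows from the order of the text and the definition of the counts, and needs no assumed number.

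The size does rest on assumptions. The adjustment can remove an effect carried by PHQ-9 frequency entirely: roughly 0.6 to 1.0 points, or 0.12 to 0.21 SD, to about 0. It can produce a spurious effect in either direction when completion or attendance shares a prognostic factor with outcome. It does no more than cost precision when no such factor is shared and recording has no effect, and it gives no bias when recording and sessions are equal across arms. The illustrations show possible size and sign and do not predict this trial's result.

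**What to change.** State in C13a that the H1b/H3 arm contrast is taken from the step with implementation group and no session counts, and say how group enters with respect to time so that the coefficient is a difference in change.

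Report the model with the counts separately, labelled as the exploratory fidelity analysis. Count only sessions up to the week-12 assessment. Preferably enter number of sessions with the proportions of sessions recorded and discussed, in place of three overlapping counts. State that its group coefficient is not interpreted as the effect of implementation condition.

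The cost is SAP wording and one separately labelled model. No new data are needed. The Aim 3 text is in the past tense and already reports 22.8% missing week-12 interviews, so the clarification should also say which step was used for any arm result already reported.

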### **Clients**

Clients seeking treatment for depression at the 12 enrolled Centerstone sites will be recruited for participation in the proposed research during Phase 2 of the study (months 8 to 38; we will stop recruitment at month 35 to allow for the necessary 12 week assessment to be completed during Phase 2). Approximately 625 clients will be recruited (given the potential for unplanned attrition) to achieve our goal enrollment of 500 clients (an average of 42 per site, 3 per clinician) based on power analyses.

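### The Aim 3 detectable correlations come without a test, N, power or parameter, fit the recruitment numbers better than the planned ones, and do not reflect that H3 compares arms randomised over 12 sites

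*Combined protocol and SAP*

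**What the plan says.** The power paragraph of C13a treats the three aims differently.

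- **Aim 1.** Monte Carlo simulation in which "power is the proportion of significant effects (2-tailed" .05), with the goal of "identifying the smallest detectable effect size with power" above 80%. The site ICC is .05. Detectable d is .46 at N = 150 clinicians and .30 at N = 500 clients.
- **Aim 2.** The same assumptions, but with effective sample sizes: "an ICC corrected sample size) based on a design effect adjustment".
- **Aim 3.** "For Aim 3 analyses, we are sufficiently powered to detect effect sizes as small as" r = .27 (clinicians) and r = .21 (clients). No N, test, power or parameter is attached.

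The paragraph closes by calling the planned sample sizes sufficient throughout, with site as a random effect and 6 sites per condition.

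H3, in Section A and again in C13a, is the tailored versus standardized comparison of depression change from intake to week 12. The analysis: "Depression severity was analyzed using linear mixed models with Satterthwaite degrees of freedom implemented using the R lmerTest package". The model has random intercepts for patient and clinic. Then: "Next, implementation group was added to the model". Three client-level counts follow: sessions, sessions with the PHQ-9 recorded, and sessions with it discussed.

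On numbers, Section V.C says: "Approximately 625 clients will be recruited (given the potential for unplanned attrition) to achieve our goal enrollment of 500 clients". For clinicians the corresponding figures are 187 and 150.

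**The concern.** A detectable effect size can be checked only if the reader knows which test, sample size and parameter it refers to. Here all three must be inferred, and the inference raises three problems.

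1. The printed values fit the recruitment numbers, which include people the plan expects to lose, better than the numbers it plans to have.
2. A correlation between two individual-level variables is not the H3 comparison. Condition varies only between sites, so with 12 sites the arm test has about 10 degrees of freedom, however many clients are enrolled.
3. The clinician figure belongs to no Aim 3 analysis that the plan describes.

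The stake is how a null H3 would be read. C14 says that an unsupported hypothesis would show that customization harms outcomes. That reading is weaker still if the chance of missing the advertised effect is larger than readers assume.

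**Working it through.** **Inputs.** Two-sided .05 and 80% power (stated for Aim 1, assumed here for Aim 3). Site ICC .05 (Aim 1). Design-effect correction (Aim 2, assumed carried over). 12 sites, 6 per condition, assumed equal in size. N = 150 and 500 planned; 187 and 625 to be recruited.

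**Step 1: reproduce the printed figures.** Effective n = N / [1 + (N/12 − 1) × .05]. Detectable r by Fisher z = tanh[(1.960 + 0.842) / √(effective n − 3)]. The t-test form is the ordinary test of a correlation on the same effective n.

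| Group | N | Design effect | Effective n | r, Fisher z | r, t-test form |
|---|---|---|---|---|---|
| Clinicians, recruited | 187 | 1.729 | 108.1 | .267 | .262 |
| Clinicians, planned | 150 | 1.575 | 95.2 | .284 | .279 |
| Clients, recruited | 625 | 3.554 | 175.8 | .210 | .208 |
| Clients, planned | 500 | 3.033 | 164.8 | .217 | .214 |

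Fisher z at 187 and 625 gives both printed values, .27 and .21. At 150 the clinician value rounds to .28 in both forms. At 500 the client value rounds to .22 by Fisher z but to .21 by the t-test form. Without a design effect, 150 and 500 would give .227 and .125, so a clustering correction was evidently used.

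**Step 2: power of the printed r at the planned N.** By Fisher z, power = Φ[atanh(r) × √(effective n − 3) − 1.960].

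- Clinicians, r = .27, N = 150: 75.8% (Fisher z), 77.3% (t-test form).
- Clients, r = .21, N = 500: 77.4% (Fisher z), 78.3% (t-test form).

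**Step 3: H3 as an arm contrast.** This step assumes that r = .21 is the correlation of arm with the week-12 score.

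- d = 2r / √(1 − r²) = .42 / .9777 = .43.
- Noncentrality = d × √164.8 / 2 = 2.758.
- Degrees of freedom 12 − 2 = 10; critical value 2.228.
- Power = 70.1%. The normal approximation gives 78.7%, so most of the loss comes from the degrees of freedom and little from the choice of N. At N = 625 with no loss, power is still only 72.8%.

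Power over an assumed range of ICC (N = 500, 10 df):

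| ICC | Power |
|---|---|
| .02 | 89% |
| .03 | 83% |
| .05 | 70% |
| .08 | 56% |

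Baseline adjustment, with an assumed baseline to week-12 correlation of .5: the unadjusted variance of a site mean is .05 + .95/41.67 = .0728. If adjustment removes a quarter (.5²) of the within-site part only, it becomes .0671 and power is about 74%. If it also removes a quarter of the between-site part, it becomes .0546 and power is about 82%.

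**Step 4: size detectable with 80% power.** On 10 df the noncentrality must be 3.110. At N = 500 and ICC .05, unadjusted, d = 2 × 3.110 / √164.8 = .48, and r = d / √(d² + 4) = .235.

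**The case against.** **Aim 3 states no 80%.** That target is given for the Aim 1 simulations only. This stands, and the percentages above depend on carrying it over.

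**The correlation may not be meant for the arm contrast.** Section A describes Aim 3 as exploring how MBC fidelity affects client outcomes, and the model includes client-level counts. A correlation suits those, while the Aim 1 contrasts are given as d. This also stands. For such counts the 10-df penalty would be smaller. It leaves H3, the only hypothesis stated for Aim 3, without a power statement.

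**70% is not the plan's own test.** The model covers change from intake to week 12, and the text does not say whether group enters as a main effect or as an interaction with time. With a group-by-time term and random intercepts only, the clinic intercept cancels from within-patient change. Taking the repeated-measures ICC of .50 and a difference in change of d = .43, power at about 482 completers (625 less 22.8%; the documents do not report that 625 enrolled) is d × √482 / 2 = 4.72, or about 99.7%. So 70% is not a unique answer. But that model assumes that sites do not differ in change, which is a strong assumption when sites are what was randomised.

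**The N inference is indirect.** The client figure cannot separate 500 from 625. Even for clinicians, an assumed site size of 10 (with 40 clients per site) would give .27 and .21 by Fisher z at 150 and 500. The stated 12 sites imply 12.5 and about 42, however. The N printed under Aim 1 is 150 and 500.

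**All participants are kept through multiple imputation.** True, but imputation does not restore the information lost, and Section V.C presents 625 as the allowance needed to reach 500.

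**Aim 3 is secondary and exploratory, and the N discrepancy is only about .01 to .02 in r.** Both are so, which is why a rewording suffices.

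**Conclusion.** The Aim 3 power sentence cannot be tied to an analysis, and no clinician-level Aim 3 outcome model exists for r = .27 to refer to. Neither finding needs an assumption.

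Under the section's own assumptions, the clinician figure is slightly optimistic at the planned 150: .28 rather than .27. The client figure at 500 is borderline.

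For H3, about 70% power at r = .21 is conditional. It requires r to be the week-12 arm effect, ICC .05, equal sites, about 10 df and no baseline adjustment. Across the alternatives shown for that week-12 contrast, power runs from 56% to 89%.

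A reader might infer two stronger claims that the documents do not support. One is that the plan promises 80% power for H3 and delivers 70%. It attaches no power to Aim 3 and never links r to the arm contrast. The other is that both figures prove that pre-attrition numbers were used. The client figure does not show this, and the test itself is inferred by back-calculation.

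**What to change.** In the power paragraph of C13a, replace the Aim 3 sentence so that it does the following.

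1. Names the test, N, power and parameter behind each figure, at the planned N. If correlations with the fidelity counts are meant, label them so and give about r = .28 (N = 150) and r = .22 (N = 500).
2. Gives H3 separately as an arm contrast with site-level degrees of freedom: 80% power at about d = .48 (r = .235) for N = 500, ICC .05, unadjusted. Add a range over ICC and baseline correlation. Say whether group enters as a main effect or as a group-by-time term, and recompute if the fitted model differs from a week-12 contrast.
3. Deletes the clinician figure, or ties it to a stated analysis.

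The cost is a short rewording and a small recalculation. The stated detectable sizes become slightly less favourable. No further clients, clinicians or data are needed.
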